## 11.2 CHOICE OF SAMPLE SIZE

The choice of sample size was based on expert opinion; we conjecture that 18 participants may be sufficient to provide adequate precision for the estimators of variance components and other parameters for which information is needed to plan a future study. As a rough and indirect assessment of the precision afforded by studying a sample of 18 subjects, we considered that an estimate of the proportion of subjects in the target population that would experience a greater increase in MEP amplitude with active tDCS, relative to sham: for an observed estimate of 50%, the 95% confidence interval would span  $[50\% \pm 20\%]$ . Or, if 80% was the observed estimate, then the 95% CI would span  $[80\% \pm 16\%]$ .

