### 3 SUBJECT SELECTION AND WITHDRAWAL

A total of 18 participants will be recruited for this study and all data will be collected at UNC-CH. No specific plans have been made to enroll participants from vulnerable populations.

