#### 4.1 TREATMENT ASSIGNMENT PROCEDURES

Each participant will experience all three versions of tDCS (anode, cathode, sham). There are 6 ways to order the three tDCS treatments: ACS, ASC, CAS, CSA, SAC, SCA. By randomization, each participant will be assigned to one of these sequences. Three participants will be assigned to each of these 6 sequence groups. (The 6 sequences comprise two Latin squares). Each session has 1-day gap to remove outlasting effects. The randomization schedule will be computed prior to recruitment of subjects and the random assignments will be concealed from the personnel who screen potential participants until the moment that the participant is enrolled and ready for baseline evaluations. To accomplish this, the randomization schedule will be used to create a set of sequentially-numbered opaque sealed envelopes (SNOES).

ACS: Anode → Cathode → Sham (3 participants)

ASC: Anode → Sham → Cathode (3 participants)

CAS: Cathode → Anode → Sham (3 participants)

CSA: Cathode → Sham → Anode (3 participants)

SAC: Sham → Anode → Cathode (3 participants)

SCA: Sham → Cathode → Anode (3 participants)

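### Section 11.2: the 95% confidence intervals quoted for 18 participants are too narrow; ±20 and ±16 points are what 24 participants would give

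*Combined protocol and SAP*

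**What the plan says.** Section 11.2 does not derive the sample size from a calculation: "The choice of sample size was based on expert opinion". It then offers one numerical check, introduced as follows: "As a rough and indirect assessment of the precision afforded by studying a sample of 18 subjects". The quantity used is the "proportion of subjects in the target population that would experience a greater increase in MEP amplitude with active tDCS, relative to sham". Two 95% intervals are given:

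- "for an observed estimate of 50%, the 95% confidence interval would span" 50% ± 20%;
- "if 80% was the observed estimate, then the 95% CI would span" 80% ± 16%.

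The sample size is the same elsewhere. Section 3 states: "A total of 18 participants will be recruited for this study". Section 4.1 reaches the same total through the six sequences: "Three participants will be assigned to each of these 6 sequence groups". Every participant receives all three conditions, so the active-versus-sham comparison is made within each person and the proportion has a denominator of 18. The documents mention no other sample size and no other precision or power calculation.

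**The concern.** An interval written as an estimate plus or minus a fixed amount is normally the Wald interval. With 18 people its half-width at 50% should exceed 23 points, so a stated 20 looks wrong at once.

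The two intervals are the whole of the quantitative case for 18 participants, and the study exists to supply estimates for planning a later one (Aim 3). A reader of Section 11.2 would believe that the pilot is as precise as a study one third larger. The error affects what is claimed for the design. It does not affect the intervals that will be computed from the data.

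**Working it through.** **Inputs.** n = 18 (Sections 3, 4.1 and 11.2); confidence level 95% and observed proportions 0.50 and 0.80 (Section 11.2); stated half-widths 0.20 and 0.16 (Section 11.2). The plan names no interval method, so the Wald form is assumed first and others are tried afterwards.

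**Step 1: try to reproduce the plan's figures.** Half-width = 1.96 × √(p(1 − p)/n).

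- p = 0.50: 1.96 × √(0.25/18) = 0.231, so 50% ± 23.1% (26.9% to 73.1%). The plan says ± 20%.
- p = 0.80: 1.96 × √(0.16/18) = 0.185, so 80% ± 18.5% (61.5% to 98.5%). The plan says ± 16%.

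Neither is reproduced.

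**Step 2: find the n that the stated figures imply.** n = 1.96² × p(1 − p)/h², using the unrounded normal quantile.

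- From ± 20% at 0.50: 3.8415 × 0.25/0.0400 = 24.01.
- From ± 16% at 0.80: 3.8415 × 0.16/0.0256 = 24.01.

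At n = 24 the Wald half-widths are 20.0 and 16.0 points, exactly the stated pair. If the stated values were rounded to whole points, the implied n runs from 22.9 to 25.3 (50% case) and from 22.6 to 25.6 (80% case). Rounding therefore cannot bring n down to 18.

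**Step 3: try other 95% methods at n = 18.** Half-widths are in percentage points. The 80% column uses 14.4 successes as a notional count.

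| Method | At 50% | At 80% |
|---|---|---|
| Plan | 20 | 16 |
| Wald | 23.1 | 18.5 |
| Wald, continuity-corrected | 25.9 | 21.3 |
| Wald with t quantile | 24.9 | 19.9 |
| Wilson | 21.0 | 17.6 |
| Agresti-Coull | 21.0 | 18.2 |
| Jeffreys | 21.6 | 17.7 |
| Uniform prior | 21.1 | 17.7 |
| Clopper-Pearson (exact) | 24.0 | 20.0 |

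Mid-P gives 22.2 at 9/18, and 18.9 or 17.3 at 14/18 or 15/18. No method gives 20 and 16. The Wilson interval at 80% is 57.1% to 92.3%, which is not centred on 80% and so would not be written with a ± sign.

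**Step 4: try a different level or denominator.** A 90% Wald interval at n = 18 gives 19.4 and 15.5, which is not the pair. At n = 18 the stated half-widths correspond to about 91% confidence. Counting each person once per active condition (n = 36) gives 16.3 and 13.1, which does not match either.

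**Step 5: exact intervals at counts that can occur.** With 18 people an observed 80% would be 14.4 people; the neighbouring values are 14/18 = 77.8% and 15/18 = 83.3%. The Clopper-Pearson 95% intervals are:

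- 9/18: 26.0% to 74.0%
- 14/18: 52.4% to 93.6%
- 15/18: 58.6% to 96.4%

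**The case against.** The arithmetic cannot be defended, but several points limit its weight.

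- **The check did not set the sample size.** The plan bases 18 on expert opinion, conjectures that it may be enough, and labels the intervals as rough and indirect. No test, endpoint or stopping rule depends on them. This stands: the error does not show that 18 is a poor choice for a pilot.
- **Planning of the future study is not harmed directly.** Section 11.1 stresses uncertainty, but it means the intervals to be tabulated from the study's own data. Those will be right whatever Section 11.2 says. This stands too.
- **The size of the error depends on the method.** The figure of about 15% applies to Wald. Against Wilson the gap is about 5% at 50% (21.0 against 20) and 10% at 80% (17.6 against 16). Against Clopper-Pearson it is about 20% and 25%. This is fair, but every method tried moves the figure in the same direction.
- **80% is a round illustrative value.** That 18 people cannot yield exactly 80% is a minor matter. It is a reason to prefer attainable counts when exact limits are quoted, and no more.
- **The origin of the figures is unknown.** The match to n = 24 is numerical. The documents do not mention a 24-person plan, and none should be inferred.

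None of this makes the stated intervals correct for the stated n and confidence level.

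**Conclusion.** The concern holds. At 95% confidence and n = 18 the Wald half-widths are 23.1 and 18.5 points. The plan's 20 and 16 understate them by 3.1 and 2.5 points; the correct values are wider by a factor of √(24/18) = 1.155. The stated precision would need 24 participants.

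The sizes assume the Wald form, which the ± notation suggests, and all 18 participants contributing. With one lost (n = 17) the half-widths become 23.8 and 19.0. The conclusion that the stated pair is wrong does not depend on the Wald assumption, since no 95% method tried reproduces it.

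The statement should be corrected because it is false as written and is the only numerical support for the sample size. The consequence for the conduct and analysis of the study is small.

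**What to change.** In Section 11.2, replace the two intervals with values for n = 18 and name the method. Either of these would do:

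- Wald: 50% ± 23% and 80% ± 18% (23.1 and 18.5 points to one decimal);
- preferably, Clopper-Pearson at attainable counts: 9/18, 26% to 74%; 14/18, 52% to 94%; 15/18, 59% to 96%.

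An optional addition would speak to the stated purpose, which is variance components. With complete data, 18 × 3 = 54 observations, and the full model in Section 11.1 leaves 53 − 5 (sequence) − 12 (subjects within sequence) − 2 (period) − 2 (condition) − 2 (carryover) = 30 residual degrees of freedom. Under normal errors the 95% interval for the within-subject variance then runs from 0.64 to 1.79 times its estimate.

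The between-subject mean square, on 12 degrees of freedom, has limits of 0.51 to 2.72 times its estimate. If this is quoted it must be labelled as a mean square. Under compound symmetry it estimates the within-subject variance plus three times the between-subject variance, so these are not limits for the between-subject component or the intra-class correlation. Both sets of limits change if data are missing or model terms are dropped, as the sensitivity analyses allow.

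The cost is a change of wording and a slightly less favourable statement of precision. Enrolment, design and analysis stay as they are.

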## 11.3 DATA MANAGEMENT

Data will be stored in a password-protected cloud-based data system that does not contain any participant information. Individual records are referred to by dummy identifiers that cannot be traced back to the study participants except with the master code list that is stored separately in a secured location.

## 12 DATA HANDLING AND RECORD KEEPING

The study coordinator and research assistants are responsible for the accuracy, completeness, legibility, and timeliness of the data reported.

### 12.1 PHI AND HIPAA

Information about study participants will be kept confidential and managed according to the requirements of the Health Insurance Portability and Accountability Act of 1996 (HIPAA). Those regulations require a signed subject authorization informing the subject of the following:

- What protected health information (PHI) will be collected from the participants in this study
- Who will have access to that information and why
- Who will use or disclose that information
- The rights of a research subject to revoke their authorization for use of their PHI.

In the event that a participant revokes authorization to collect or use PHI, the investigator, by regulation, retains the ability to use all information collected prior to the revocation of participant authorization. For participants that have revoked authorization to collect or use PHI, attempts should be made to obtain permission to collect at least vital status (i.e., that the subject is alive) at the end of their scheduled study period.

### 12.2 CONFIDENTIALITY

---

#### 12.2.1 ACCESS TO SOURCE DOCUMENTS

The research coordinator, research assistants, and PI will have access to all of the source documents collected over the course of the study. The Co-I and medical monitor will have access to files upon request, as they will need access to the locked rooms and filing cabinets in which these documents are located.

Data will stay on a password-protected computer. Subsequently, a copy will be processed on a separate, password-protected desktop computer in the [name] Lab ([name]).

---

#### 12.2.3 OTHER

Please note that there is no significant risk of deductive disclosure in this study. In addition, none of the groupings or subgroupings used in analysis will be small enough to allow individuals to be identified.

### 12.3 SOURCE DOCUMENTS

Source data is all information, original records of clinical findings, observations, or other activities in a study necessary for the reconstruction and evaluation of the trial. Source data are contained in source documents. Source data include:

#### **PARTNERS HUMAN RESEARCH COMMITTEE (IRB).**

- All IRB correspondences are documented
- The study staff is IRB approved prior to performing any study procedures
- All versions of the IRB protocols and informed consent forms are on file

**INFORMED CONSENT.**

- Ensure that participant identification is not recorded on the ICF (i.e., no participant ID)
- There is documentation that the participant is given a copy of the consent form
- The participant and study representative signed and dated the consent form for him/herself
- The participant initialed and dated all appropriate pages on the informed consent form
- Note to file (Appendix D) made for any informed consent deviations
- Ensure a valid (current version date) copy of the consent form was used

**PROTOCOL DEVIATIONS.**

- Any and all protocol deviations (exceptions and violations) are documented in the participant folder and reported to the IRB as required

**OTHER SOURCE DOCUMENTS.**

- Each participant folder will contain a checklist to ensure that all source documents are administered and collected properly. The checklist will be dated by the researcher for each time an assessment is administered
- Review participant folders to ensure the accuracy, completeness, and legibility of the data.
- Any correction made to the source documents is dated, initialed, and explained. The original entry should not be obscured.
- The protocol-specific source documents are on file.
- Source documents are completed in ink.
- Note to files (Appendix D) are made for missing or incomplete data and to explain any discrepancies or additional comments.

#### 12.4 DATA MANAGEMENT RESPONSIBILITIES

The responsibilities designated to each member of the research team are documented on the Delegation of Authority Form. The study coordinator and research assistants will be responsible for the informed consent process, review for eligibility, questionnaire administration, data entry, device administration, EEG administration, and CRF entries. The study coordinator will be responsible for documentation and reporting, while the PI will be responsible for review of the documentation forms, and overview of the research staff.

#### 12.5 DATA CAPTURE METHODS (REDCAP)

All data will be entered into a data capture system provided by REDCap. The data system includes password protection and internal quality checks, such as automatic range checks, to identify data that appear inconsistent, incomplete, or inaccurate. Clinical data will be entered directly from the source documents.

All assessments completed by the participant at home will be completed via REDCap as well, ensuring participant security and confidentiality.

#### 12.6 PROTOCOL DEVIATIONS

All deviations from the protocol will be addressed in study participant source documents. The researcher will complete a Protocol Deviation Log using the participant code as the identifier. This form will collect information such as the date the deviation occurred, details of what the deviation consisted of, any corrective and preventative actions that were taken as a result of the deviation, and the date that the PI and IRB were notified. The PI will

review the information and initial once approved. A completed copy of the Protocol Deviation Form will be maintained in the regulatory file, as well as in the participant's source document. Protocol deviations will be sent to the IRB per their guidelines. The site PI/study staff will be responsible for knowing and adhering to their IRB requirements.

## 12.7 RECORD RETENTION

According to the University of North Carolina at Chapel Hill's Archives and Record Management Services schedule for General Records Retention and Disposition Schedule 6.10, records will be kept for 5 years after the completion of the study or grant end date, whichever is later.

## 13 ETHICAL CONSIDERATIONS

### 13.1 ETHICAL STANDARD

The investigator will ensure that this study is conducted in full conformity with the principles set forth in the Belmont Report: Ethical Principles and Guidelines for the Protection of Human Subjects of Research, as drafted by the US National Commission for the Protection of Human Subjects of Biomedical and Behavioral Research (April 18, 1979) and codified in 45 CFR Part 46 and/or the ICH E6; 62 Federal Regulations 25691 (1997).

### 13.2 INSTITUTIONAL REVIEW BOARD (IRB)

The Office of Human Research Ethics is responsible for ethical and regulatory oversight of research at UNC-Chapel Hill that involves human participants. The OHRE administers, supports, and guides the work of the Institutional Review Boards and all related activities. Any research involving human participants proposed by faculty, staff, or students must be reviewed and approved by an IRB before research may begin, and before related grants may be funded. OHRE and the IRBs are critical components of the coordinated Human Research Protection Program, which serves to protect the rights and welfare of human participants. All components of this program must work together to ensure institutional compliance with ethical principles and regulatory requirements. The following is a mission statement for the coordinated Human Research Protection Program:

The University of North Carolina at Chapel Hill is committed to expanding and disseminating knowledge for the benefit of the people of North Carolina and the world. An important part of that commitment to knowledge is research of the highest quality on all aspects of the health and behavior of people, and such research is only possible through the participation of humans as research participants. Human participants are partners in research and a precious resource to the university. At UNC-Chapel Hill, human participant research is a privilege, but not a right. Consistent with that philosophy, it is the mission of the UNC-Chapel Hill Human Research Protection Program to ensure that:

- a. The rights and welfare of human participants are paramount in the research process;
- b. The highest standards of ethical conduct are employed in all research involving human participants;
- c. Research investigators are properly trained in the ethical and regulatory aspects of research with human participants;
- d. Research investigators deal honestly and fairly with human participants, informing them fully of procedures to be followed, and the risks and benefits of participating in research; and
- e. Research using human participants at UNC-CH conforms to applicable local, state, and federal laws and regulations and the policies of the university.

### 13.3 INFORMED CONSENT PROCESS

Informed consent is a process that is initiated prior to the individual's agreeing to participate in the study and continues throughout the individual's study participation. Extensive discussion of risks of TMS and tDCS will be provided to the participants. Consent forms describing, in detail, the study intervention, device, procedures, and risks are given to the participant and written documentation of informed consent is required prior to the administration of any assessments used in this study. All consent forms will be IRB-approved and updated with any new information as modifications are made throughout the study.

Together, the researcher and potential participants will review the study in its entirety by reviewing the consent form together in a private location. At several intervals during the consent review, the researcher will ask the

participant questions that will assess the comprehension of the information in the consent. If the participant is unsure or does not know, the researcher will return to that section and more carefully explain the information. Participants must sign the informed consent document prior to any procedures taking place. If needed, the participants will have the opportunity to discuss the study with their surrogates or think about it prior to agreeing to participate. Participants may withdraw consent at any time throughout the course of the trial. A copy of the informed consent document will be given to the participants for their records.

#### 13.4 EXCLUSION OF WOMEN, MINORITIES, AND CHILDREN (SPECIAL POPULATIONS)

Non-English speaking individuals are excluded because the ability to accurately and complete communicate study information, answer questions about the study, and obtain consent is necessary. Pregnant participants will be excluded despite the fact that theoretical risk to mother or fetus is exceedingly small, since no safety data for pregnancy is known to exist for transcranial magnetic/electrical stimulation studies.

#### 13.5 PARTICIPANT CONFIDENTIALITY

Participant confidentiality is strictly held in trust by the participating investigators, their staff, and the research team. This confidentiality is extended to cover testing of biological samples and genetic tests in addition to the clinical information relating to participants.

All data will only be referenced by dummy identifier code. Data will be stored on a password protected computer. A key connecting names and code numbers will be kept in a locked cabinet, accessible only by research personnel. All data will be stored and analyzed on password protected computers, also only accessible by research personnel. Participants will not be identified in any report or publication about this study. See *10 Data Handling and Record Keeping* for more information on source documentation storage and security.

#### 13.6 STUDY DISCONTINUATION

In the event that the study is discontinued, participants who have completed or who are still enrolled in the study will be notified. Any new information gained during the course of the study that might affect participant's willingness to continue will be communicated within 2 days of the PI learning this information.

### 14 PUBLICATION POLICY

There are no restrictions on publications since this is an investigator-initiated study funded by a grant agency that has no influence on the publications resulting from this study.

**APPENDIX A: SCHEDULE OF EVENTS**

A detailed schematic describing phone screening and visit for stimulation.

Procedures	Phone Screening	Stimulation
Provide Verbal Consent	x	
Signed Consent Form		x
Assessment of Eligibility Criteria	x	x
Review of Medical History	x	x
Review of Concomitant Medications	x	x
Stimulation		x
Stimulation Questionnaire		x

## APPENDIX D: NOTE TO FILE

IRB#: 17-0149

PI: [name]

Study Title: [Insert Short Name]

Researcher: \_\_\_\_\_

Date of Occurrence: \_\_\_\_\_

Participant ID: \_\_\_\_\_

CONFIDENTIAL

Great! This study is looking at motor activity in your hand caused by weak brain stimulation in healthy individuals. Findings from this study will help the development of new study using magnetic and electrical stimulations. In this study, a very weak electric current will be applied to your scalp. Some people report a mild tingling because of this stimulation, but no other side effects have been found. It is not a shock and should cause no pain.

Participation in this study includes only one session, which is stimulation session. You will be compensated for your time spent participating in the study. The maximum compensation for this study is XXXXXXX for completing one-day session. Are you still interested in participating?

*(If 'No', thank them for their time; if 'Yes', proceed)*

Great! In order to make sure you're eligible for the study, I need to ask you a few questions. Please answer yes or no. You do not need to provide any further details.

*(If the answer given is not the same as the answer shown, thank the individual for his or her interest and say, unfortunately, they do not qualify for the current study)*

- Are you between 18 to 50 years old? (Yes)
- Have you ever, or are you currently being treated for a neurological condition (e.g., epilepsy, migraines)? (No)
- Are you currently taking medication for the treatment of chronic pain or any other psychiatric illness? (No)
- Have you ever had brain surgery? (No)
- Do you have any brain devices or implants, including a cochlear implant or aneurysm clip? (No)
- Have you ever been diagnosed with a traumatic brain injury? (No)

Phone Screening:
 
 Pass
 
 Fail
 
Reason for failing: _____
 
_____
 
_____
 
Initials _____

--

You are eligible for participation in the stimulation session of the study.

Scheduled Stimulation Session
 
Date: _____
 
Time: _____

---

I will send you an email confirming this time, and providing directions on how to find the specific location of your session. We will also send you an email to confirm your appointment 24 hours beforehand. Please respond to this email so we know you are still coming. If you have any questions before then, please don't hesitate to contact us at this phone number or at [name]\[contact]. Thank you for your time.

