### 5.1 SCREENING

- Screening via a telephone call

The phone screening allows researchers to screen out participants based on self-report responses and for potential participants to become familiar with the study schedule, including procedures. During the telephone screening, researchers will provide a brief background about TMS, tDCS, and EEG. The timeline will be explained to the participants and the participant will be informed of compensation, both amount and payment schedule. The participant will be asked if they have any questions. Once all questions have been answered, the participant will be asked if he/she is still interested in participating in the study. If yes, the researcher will ask if the participant will provide verbal consent to begin the initial phone screening which will determine eligibility for the stimulation session. *A telephone script, which includes the screening questions, is provided in Appendix E.* If the participant meets initial criteria with these two assessments, the stimulation session will be scheduled and a reminder call or email will be given at least 24 hours before the stimulation session.

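### The telephone script tells callers there is one session and no side effect beyond tingling, while the design needs three sessions and Section 8.2 also reports burning, itching and headache

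*Combined protocol and SAP*

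**What the plan says.** Section 5.1 describes the screening call. It says "The timeline will be explained to the participants and the participant will be informed of compensation, both amount and payment schedule", and it names the tool for the call: "A telephone script, which includes the screening questions, is provided in Appendix E". For callers who pass, "the stimulation session will be scheduled and a reminder call or email will be given at least 24 hours before the stimulation session".

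The contents list and Section 5.1 place the script in Appendix E. In the text available for review it follows the Appendix D note-to-file form. It says:

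- on commitment: "Participation in this study includes only one session, which is stimulation session";
- on pay: "The maximum compensation for this study is XXXXXXX for completing one-day session";
- on side effects: "Some people report a mild tingling because of this stimulation, but no other side effects have been found";
- on passing the screen: "You are eligible for participation in the stimulation session of the study", followed by one date field and one time field;
- on confirmation: "I will send you an email confirming this time, and providing directions on how to find the specific location of your session".

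The design is stated differently elsewhere. The Study Summary and Section 4 describe a crossover with three conditions, three sessions and six sequences. Section 4.1 has every participant receive anode, cathode and sham, and Sections 4 and 4.1 set a 1-day gap between sessions. Section 11.1 models three periods per participant. Section 8.2, under physical risks, lists tingling, burning and itching at the electrodes, and headache. It describes the skin sensations as mild and passing, and says it is unclear whether stimulation caused any of these effects.

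**The concern.** The script is what a volunteer hears before deciding whether to go on. Directly after the statements on sessions and pay, the caller is asked whether he is still interested. If staff read it as written, he agrees to go on believing that he owes one visit on one day and that only tingling has been reported. Both beliefs conflict with the protocol.

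The staff instruction does not repair this, because Section 5.1 also schedules a single session. The same singular wording recurs in Section 3.3.2 (payment and reminder), Section 5.2 (consent), Section 7.3 (compliance) and Appendix A (one stimulation column). The design sections are clear about three sessions, but the operational text around them has not been brought into line.

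What is at stake is the accuracy of what volunteers are told at first contact and, in practice, refusals or rebooking when the real commitment comes out at the consent visit.

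**Working it through.** No sample-size or power formula applies. The check is to fix the number of sessions that the design needs and set the script beside it.

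**1. Sessions implied by the analysis plan.** Section 11.1 gives 75 amplitudes before and 75 after each of 3 conditions, and 450 per subject.

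75 × 2 × 3 = 450, which matches the stated figure.

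With one condition per session, as the three-session design has it, a single session would give 75 × 2 = 150 of the 450. The count of 75 per block is taken as stated; the factor of 3 does not depend on it.

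**2. Can three sessions be one day?** No. Sections 4 and 4.1 put a 1-day gap between sessions, so a commitment to one day cannot cover all three. Section 4 also refers to a participant's visits in the plural, and Section 3.3.2 plans for one staff member to handle all of a participant's sessions. Three sessions is therefore the intended design, and the script is what departs from it.

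**3. Script against protocol.**

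| Item | Script | Rest of the protocol | Covered |
|---|---|---|---|
| Sessions | one | three (Study Summary, Sections 4, 4.1, 11.1) | 1 of 3 |
| Days tied to maximum pay | one | sessions on separate days (Sections 4, 4.1) | one day only |
| Appointment dates recorded | one | three needed | 1 of 3 |
| Side effects named | tingling | tingling, burning, itching, headache (Section 8.2) | 1 of 4 |

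**4. Other single-session wording.**

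- Section 3.3.2: one payment, made at the stimulation session, and a reminder for that session.
- Section 5.1: one session scheduled.
- Section 5.2: consent at the stimulation session.
- Section 7.3: compliance defined by attending a session, in the singular.
- Appendix A: one stimulation column, introduced as a visit.

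Some of these can be read as compatible with three sessions, for example a single payment at the last one or a column that repeats. Left alone, however, they would still sit badly with a corrected script.

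**5. Effect on the statistics.** None. Correcting the script changes no stated trial figure: 18 participants, three periods and 450 amplitudes per subject all stay.

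**The case against.** The best defence is that the call comes before consent and the consent process is thorough. Section 3.3.2 requires a check that participants understand how long participation lasts. Section 13.3 requires a full discussion of risks, a review of the whole study with comprehension questions, and a signature before any procedure. A side-effect questionnaire follows each stimulation. This stands, and it limits the harm. It does not justify a wrong statement at first contact in the text that Section 5.1 names for the purpose.

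On side effects, the defence is that Section 8.2 calls the sensations mild and leaves causation open, while the script speaks of effects caused by stimulation. That narrows the point: the sentence is an incomplete summary, and no serious effect is concealed. It is still too absolute, since it says nothing else has been found.

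The opening of the script is not in the text available for review, nor is the consent form. The point rests on sentences that are complete in themselves; an opening that mentioned three sessions would only make the script contradict itself. Nothing is inferred from the blank pay amount, which may be a template gap or a redaction.

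A reader might draw three stronger conclusions that the documents do not support:

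- *That two of every three sessions would go unbooked.* The script has one booking field but is silent on later visits, and nothing prevents booking sessions 2 and 3 at the first visit.
- *That participants would drop out and the treatment comparisons would lose precision.* No section gives a dropout rate or links dropout to the script, and the consent check would have to fail as well. Any precision loss would be an assumption.
- *That participants enter the study misinformed.* The required consent steps point the other way, and the form itself cannot be checked here.

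**Conclusion.** The concern holds as an inconsistency between the telephone script and the protocol that should be corrected. The script states 1 of 3 sessions, ties pay to one day, records 1 of 3 appointment dates and names 1 of the 4 effects in Section 8.2. It is more than clerical, because the script is the tool for explaining timeline and compensation and the statements are false or incomplete as read.

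The consequence is limited: agreement at first contact on wrong information, and possible refusal or rebooking at the consent visit. No estimand, analysis or sample size is affected. This rests on two assumptions: that staff would read the script as written, and that consent is conducted as Sections 3.3.2 and 13.3 describe.

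**What to change.** In the telephone script:

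- state three sessions on separate days, with the 1-day gap;
- state the compensation for all three;
- provide three date and time fields;
- make the eligibility and confirmation lines plural;
- replace the sentence denying other side effects with those in Section 8.2: mild tingling, burning or itching under the electrodes, and headache. The full account of risk can stay with the consent discussion.

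Elsewhere:

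- Section 5.1: schedule three sessions, with a reminder at least 24 hours before each.
- Section 3.3.2: give reminders for each session, and say at which session the single payment is made.
- Section 5.2: place consent at the first stimulation session.
- Section 7.3: define compliance as attending all three sessions.
- Appendix A: note that the stimulation column applies to three visits.

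The cost is a handful of text edits, presumably a minor IRB amendment, and possibly slightly slower recruitment once callers hear that there are three visits.
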